8.6 Off Study Criteria

- *Per Subject choice:* Subjects may be removed from study at their request. The risks of

withdrawing will be discussed, as will alternative treatment options. Those subjects who choose to withdraw while taking alemtuzumab (Campath®) will continue to have labs monitored through the 6 month off drug time point.

- *Per principal investigator decision:* Alemtuzumab (Campath®) administration will be discontinued, the subject will be followed until the event has resolved and labs have been monitored through the 6 month off drug time point if the subject develops:
 - Intolerance of alemtuzumab (Campath®) infusion as manifested by hypotension, fever, chills and/or rash that is refractory to pre-medication with anti-histamines and acetaminophen.
 - Life threatening acute hypersensitivity reactions
 - Lymphoproliferative disease or malignancy.
 - Worsening of MDS with increased numbers of blasts fulfilling a diagnosis of RAEBt or leukemia
 - Pregnancy or unwillingness to refrain from pregnancy
 - Initiation of additional immunosuppressive therapy (except steroids or CsA)
 - Initiation of the herbal supplement *Echinacea purpurea* or *Usnea barbata* (*Old Man's Beard*)
 - Failure to respond to Campath-1H therapy
 - Failure to improve with CsA after relapse.

Once off study, subjects will be referred back to their referring physician or consented to the Hematology Branch evaluation and treatment protocol (94-H-0010) for consideration for standard therapy or evaluation for eligibility for another branch protocol, depending on what is considered to be in the best interest of the subject.

8.7 Data Management

The PI will be responsible for overseeing entry of data into an in-house password protected electronic system and ensuring data accuracy, consistency and timeliness. The principal investigator, associate investigators/research nurses and/or a contracted data manager will assist with the data management efforts. All human subjects personally identifiable information (PII) as defined in accordance to the Health Insurance Portability and Accountability Act, eligibility and consent verification will be recorded in DIR's Clinical Data System (CDS) or the Laboratory of Cardiac Energetics (LCE) database. Primary data obtained during the conduct of the protocol will be kept in secure network drives or in approved alternative sites that comply with NIH security standards. Primary and final analyzed data will have identifiers so that research data can be attributed to an individual human subject participant, e.g., study-specific identifying number (SSPIN) generated by CDS or other unique code or minimum PII required for subject identification.

End of study procedures: Data will be stored in locked cabinets and in a password protected database until it is no longer of scientific value.

Loss or destruction of data: Should we become aware that a major breach in our plan to protect patient confidentiality and trial data has occurred, the IRB will be notified.

No data will be sent outside NIH without prior IRB approval and an executed MTA or CTA.

Publication Policy: Given the research mandate of the NIH, patient data including the results of testing and responses to treatment will be entered into an NIH-authorized and controlled research database. Any future research use will occur only after appropriate human subject protection

institutional approval such as prospective NIH IRB review and approval or an exemption from the NIH Office of Human Subjects Research (OHSR).

9.0 DATA AND SAFETY MONITORING

9.1 Safety Monitoring

Principal investigator: Accrual, efficacy and safety data will be monitored by the PI.

NHLBI IRB: Accrual and safety data will be reviewed annually by the Institutional Review Board (IRB). Prior to implementation of this study, the protocol and the proposed patient consent and assent forms will be reviewed and approved by the properly constituted Institutional Review Board (IRB) operating according to the Title 45 CFR 46. This committee must approve all amendments to the protocol or informed consent, review all SAEs, and conduct continuing annual review so long as the protocol is open to accrual or follow up of subjects.

NHLBI DSMB: The NHLBI Data safety and Monitoring Board will review the protocol at 6 to 12 month intervals. A progress report will be forwarded to the DSMB at these times and their recommendations will be expeditiously implemented. The DSMB may recommend early termination of the study for considerations of safety and efficacy.

9.2 Event Characterization and Reporting

Events include adverse events (AE), serious adverse events (SAE), protocol deviations (PD), unanticipated problems (UP), and non-compliance.

The principal investigator will review all events (AEs, protocol deviations, UPs, SAEs) to determine the seriousness, expectedness, and reportability of the event. As required and/or needed, the principal investigator will review the events with the Sponsor to make the final determination of seriousness and reportability.

9.2.1 Definitions

Adverse Event (AE): Any untoward or unfavorable medical occurrence in a human subject, including any abnormal sign (e.g., abnormal physical exam or laboratory finding), symptom, or disease, temporally associated with the subject's participation in the research, whether or not considered related to the research.

Serious Adverse Event (SAE): A serious adverse event that:

- results in death;
- is life-threatening (places the subject at immediate risk of death from the event as it occurred);
- results in in-patient hospitalization or prolongation of existing hospitalization;
- results in a persistent or significant incapacity;
- results in a congenital anomaly/birth defect; or
- based upon appropriate medical judgment, may jeopardize the subject's health and may require medical or surgical intervention to prevent one of the other outcomes listed in this definition.

Suspected adverse reaction: Suspected adverse reaction means any adverse event for which there is a reasonable possibility that the drug caused the adverse event. A suspected adverse reaction implies a lesser degree of certainty about causality than adverse reaction, which means any adverse event caused by a drug.

Serious event: An event is serious if it meets the definition of a serious adverse event (above) or if it requires immediate corrective action by a PI and/or IRB to protect the safety, welfare or rights of subjects.

Unexpected adverse reaction: An adverse event or suspected adverse reaction is considered “unexpected” if it is not listed in the investigator brochure or is not listed at the specificity or severity that has been observed; or, if an investigator brochure is not required or available, is not consistent with the risk information described in the general investigational plan or elsewhere in the current application. “Unexpected”, also refers to adverse events or suspected adverse reactions that are mentioned in the investigator brochure as occurring with a class of drugs or as anticipated from the pharmacological properties of the drug, but are not specifically mentioned as occurring with the particular drug under investigation.

Unanticipated Problem (UP): Any incident, experience, or outcome that meets all of the following criteria:

1. unexpected in terms of nature, severity, or frequency in relation to
 - a. the research risks that are described in the IRB-approved research protocol and informed consent document; Investigator’s Brochure or other study documents; and
 - b. the characteristics of the subject population being studied; and
2. related or possibly related to participation in the research; and
3. places subjects or others at a greater risk of harm (including physical, psychological, economic, or social harm) than was previously known or recognized.

Unanticipated Problem that is not an Adverse Event: An unanticipated problem that does not fit the definition of an adverse event, but which may, in the opinion of the investigator, involves risk to the subject, affect others in the research study, or significantly impact the integrity of research data. For example, report occurrences of breaches of confidentiality, accidental destruction of study records, or unaccounted-for study drug.

Protocol Deviation (PD): Any change, divergence, or departure from the IRB approved research protocol.

Non-compliance: The failure to comply with applicable NIH HRPP policies, IRB requirements, or regulatory requirements for the protection of human research. Noncompliance may be further characterized as:

1. **Serious non-compliance:** Non-compliance that:

- a. Increases risks, or causes harm, to participants.
- b. Decreases potential benefits to participants.
- c. Compromises the integrity of the NIH HRPP.
- d. Invalidates the study data.

2. **Continuing non-compliance:** Non-compliance that is recurring. An example may be a pattern of non-compliance that suggests a likelihood that, absent an intervention, non-compliance will continue. Continuing noncompliance could also include a failure to respond to IRB requests to resolve previous allegations of non-compliance.

3. **Minor (non-serious) non-compliance:** Non-compliance that, is neither serious nor continuing.

9.2.2 Adverse Events Management:

. All adverse events occurring during the study, including those observed by or reported to the research team, will be recorded. The AEs will be attributed (unrelated, unlikely, possibly, probably or definitely) to study medication and/or disease and graded by severity utilizing CTC version 2.0. A copy of the criteria can be down-loaded from the CTEP home page at <http://ctep.cancer.gov/reporting/ctc.html>.

Abnormal laboratory findings used to evaluate the safety of this protocol regimen will be collected to include any change from laboratory assessments done prior to first dose of study medication that results in a progression to a grade 3 or 4 laboratory toxicity and/or are characterized by any of the following:

- Results in discontinuation from the study
- Is associated with clinical signs or symptoms
- Requires treatment or any other therapeutic intervention
- Is associated with death or another serious adverse event, including hospitalization
- Is judged by the Investigator to be of significant clinical impact
- If any abnormal laboratory result is considered clinically significant, the investigator will provide details about the action taken with respect to the test drug and about the patient's outcome.

The laboratory toxicities will be attributed (unrelated, unlikely, possibly, probably or definitely) to study medication and/or disease and graded by severity utilizing CTC version 2.0.

Length of Adverse Event reporting: Adverse event collection will start at the baseline and continue for 6 months after the last dose of Campath and when applicable cyclosporine, after which the events will be recorded in the medical record but not abstracted to toxicity tables.

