One such novel therapy, alemtuzumab (Campath®) is a humanized IgG1 monoclonal antibody directed against the CD52 protein, which is highly expressed on all lymphoid cells and monocytes. Alemtuzumab (Campath®) produces profound and persistent lymphopenia, affecting predominantly the CD4+ T cell subset. This property has made it attractive in the treatment of a wide range of diseases including rheumatoid arthritis, multiple sclerosis, ocular inflammatory disease, lymphoid malignancies, organ allograft rejection, and in conditioning regimens in stem cell transplantation to prevent graft failure and graft-versus-host disease.

We therefore propose a non-randomized, off label, pilot, Phase I/II study of alemtuzumab (Campath®) in MDS patients who are likely to respond to immunosuppression.

Primary endpoints will be changes in peripheral blood counts (platelets, absolute neutrophil count, reticulocyte count, hemoglobin). Secondary endpoints (in transfusion-dependent patients) include improvement in the transfusion requirements (measured as decrease in the number of transfusion administered on "as needed basis"), duration of response, late effects of treatment, relapse and survival.

TABLE OF CONTENTS

- 1.0 OBJECTIVES
- 2.0 BACKGROUND
- 3.0 STUDY DESIGN
- 4.0 ELIGIBILITY ASSESSMENT
- 5.0 TREATMENT PLAN
- 6.0 CLINICAL EVALUATION
- 7.0 LABORATORY RESEARCH STUDIES
- 8.0 BIOSTATISTICAL CONSIDERATIONS
- 9.0 DATA AND SAFETY MONITORING
- 10.0 HUMAN SUBJECTS PROTECTION
- 11.0 PHARMACEUTICALS

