6.5 Long Term Follow Up After 6 Months

After the 6 month visit, subjects must be evaluated at the Clinical Center (12 months (+/- 2 month) and then yearly (+/- 2 month) thereafter for 5 years and have blood work done as detailed below. Subjects will be seen by their home physician as clinically indicated and the Clinical Center and home physician will continue to communicate.

- Physical examination
- Complete blood counts with differential (annually +/- 1 month)
- Acute care, mineral, hepatic and other panel(annually +/- 1 month)
- Reticulocyte counts (annually +/- 1 month)
- DAT (direct antibody titer) (annually +/- 1 month)
- Flow cytometry of the peripheral blood for GPI-cells (annually +/- 1 month)
- EBV and CMV PCR in the blood (at 12 months only +/- 1 month)
- Thyroid function tests (annually +/- 1 month)
- Bone marrow biopsy and aspiration with cytogenetics (at 12 months +/- 1 month and annually thereafter, as clinically indicated)
- Type and screen (annually +/- 1 month or if clinically indicated)
- Lymphocyte phenotyping (12 months (+/- 1 month) and as clinical indicated)
- If cyclosporine (CsA) is added: CsA levels will be monitored every week (+/- 3 days) for the first month and then every other week (+/- 3 days) for the remainder of the treatment period. Less frequent monitoring may occur if CsA drug level is therapeutic and steady. Dosing will be adjusted to maintain blood level of 200 – 400 ng/ml. More frequent drug serum levels may be obtained as needed to achieve constant therapeutic levels

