8.2 Secondary Endpoints

8.2.1 Transfusion-independence for red blood cells and/or platelets: ability to maintain a hemoglobin >8gm/dl and a platelet count > 20 000/ μ L without the need for transfusions for a period of 6 weeks regardless of subsequent events.

8.2.2 Overall survival which is defined as the time elapsed between time of treatment and death and will be compared between responders and non-responders. Any such comparison may be biased and needs to be interpreted cautiously.

8.2.3 Life threatening toxicity. Subjects who do not complete the treatment course because of toxicity or voluntary withdrawal will be included in analyses.

8.2.4 Overall survival and transformation-free survival, which is defined as the time elapsed (reported at 3 month intervals for the first four years, then yearly thereafter) between time of treatment, and bone marrow morphologic evidence for progression (as determined by FAB criteria), development of acute leukemia, or death will be compared between responders and non-responders. Any such comparison may be biased and needs to be interpreted cautiously.

8.2.5 Response duration will be determined as the interval between time of onset of response as outlined above, and the time of relapse or loss of response characteristic (reported at 3 month intervals for the first four years, then yearly thereafter).

8.2.6 Affects of the addition of cyclosporine. Subjects who relapse after responding to Campath will be given CsA to determine if CsA will be beneficial under these circumstances. For this protocol, CsA is investigational, subjects will be followed, data will be collected and analyzed as secondary endpoints. The number of subjects who will receive CsA cannot be predicted since it will depend on the initial response to Campath which is unknown.

Response proportion, response duration, overall survival, and transformation free survival will be determined and compared within the FAB sub-groups and International Prognostic Scoring System categories of MDS and with the results of previous studies at the NIH using h-ATG alone or CsA alone to treat the cytopenia of MDS.

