9.2.3 Serious Adverse Events Management

Serious adverse events will be attributed as definitely (clearly related to the research), probably (likely related to the research), possibly (may be related to the research), unlikely (doubtfully related to the research) and unrelated (clear not related to the research).

Treatment related SAEs (TRSAEs) are those attributed as definitely, probably, or possibly. As detailed in section 8.5 stopping rules, Death and any grade IV toxicity considered to be definitely related to alemtuzumab (Campath-1H®) will be monitored and considered for early stopping the study according to statistically determined criteria. [name], NHLBI will serve as the independent monitor who reviews the attribution of TRSAEs

Hospitalization (overnight admission) for routine supportive care (platelet or RBC transfusions) or admission from the NIH inpatient unit to the NIH ICU for routine monitoring will not be reported as a serious adverse event.

Duration of Serious Adverse Event collecting and reporting: The collection of SAEs will begin on the first day of initiation of the study drug and will continue along as the subject is on study. SAE reporting will continue as long as the subject remains on study.

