9.2.4 Reporting of Events

PI: All events will be reported to the Principal Investigator of this study

[name]., NHLBI, HB
[name]
[name]
[contact]

Reporting Timeframes to IRB Chair, Clinical Director, and/or NHLBI IRB

Serious Events

Reports to the IRB and CD: The PI must report Serious UPs, and Serious PDs to the IRB and CD as soon as possible but not more than 7 days after the PI first learns of the event via PTMS using the NIH Problem Report Form.

Reports to the IRB Chair and CD: The PI must report all SAEs that do not meet the definition of UP to the IRB chair and CD not more than 14 days after the PI first learns of the event via PTMS, using the SAE submission form.

Non-serious Events

Reports to the IRB and CD: The PI must report all UPs that are not Serious to the IRB and CD, and PDs that are not Serious to the IRB, not more than 14 days after the PI first learns of the event via PTMS using the NIH Problem Report Form.

Deaths

The PI must report all deaths (that are not UPs) to the CD as soon as possible, but not more than 7 days after the PI first learns of the event.

At continuing review, the PI will provide to the IRB a summary of:

- All UPs
- All PDs
- All AEs (except for those granted a waiver of reporting)
- If, while preparing the continuing review, the PI identifies a greater frequency or level of severity of expected adverse events than was previously identified in the protocol or investigational brochure (IB), these should be reported separately as a UP. If such an observation occurs before the time of continuing IRB review, it should be reported to the IRB and CD as a UP in the time frames noted above, and summarized at the time of continuing review.

Exclusions to data reporting:

The following Adverse Events will be captured only in the source documents and will not be reported to the IRB at the time of continuing review.

- Laboratory values that do not meet the definition of a laboratory AE listed in Section 9.2.2.
- All grade 1 events listed as expected in the investigator's brochure, package insert, and/or anticipated events.

NHLBI DSMB Reporting:

Reports of serious adverse events that are unexpected and thought to be related to the experimental drug will also be forwarded no later than seven (7) days in the case of death or life-threatening

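### Late effects are a synopsis secondary endpoint, but non-serious adverse events later than 6 months after the last Campath or cyclosporine dose stay out of the toxicity tables, and section 8.2 neither lists nor analyses late effects

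*Combined protocol and SAP*

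**What the plan says.** The synopsis lists the secondary endpoints as improvement in transfusion requirements followed by "duration of response, late effects of treatment, relapse and survival". Section 8.2, the operative list, does not contain late effects. Its one toxicity item is 8.2.3: "Life threatening toxicity. Subjects who do not complete the treatment course because of toxicity or voluntary withdrawal will be included in analyses".

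Section 6.5 requires a Clinical Center visit at 12 months "and then yearly (+/- 2 month) thereafter for 5 years and have blood work done as detailed below". The yearly work includes thyroid function, DAT, flow cytometry for GPI-deficient cells, blood counts and chemistry panels.

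Section 9.2.2 opens adverse-event collection at baseline and closes it half a year past the final Campath dose, or the final cyclosporine dose where that drug is used. For anything later it has this rule: "after which the events will be recorded in the medical record but not abstracted to toxicity tables". Serious events follow a separate rule in 9.2.3: "SAE reporting will continue as long as the subject remains on study". Under 5.2.1 and 8.6, subjects who fail to respond to Campath leave the study, as do those who do not improve on cyclosporine after relapse.

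**The concern.** A stated collection rule undercuts a stated endpoint. The plan pays for 5 years of visits and tests that look designed to detect late autoimmunity, thyroid disease and GPI-deficient clones. The adverse-event rule closes the tables before the first of the annual visits, unless cyclosporine extends the window. No section then says how anything found at those visits becomes a late-effects result.

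The protocol gives reasons to look beyond 6 months. Section 2.7.1 reports that helper T cells can stay low for years, section 2.7.4 gives CD8 recovery times of up to 36 months, and section 10.3.2 warns that cyclosporine effects may appear years later. What is at stake is interpretation: a reader of the final toxicity table could take the absence of late non-serious events as evidence that none occurred, when the plan did not call for them to be tabulated.

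**Working it through.** The plan states no figure for this point, so there is nothing of its own to reproduce. The check is a comparison of sections and some arithmetic on the length of the window.

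**Inputs**
- Treatment: 1 test-dose day plus 10 dosing days = 11 days (5.1).
- Adverse-event window: 6 months after the last dose of Campath, or of cyclosporine when given (9.2.2).
- Follow-up: 60 months, or 72 if the 5 years in 6.5 run from month 12.
- Cyclosporine after relapse: 2–3 months or longer, at the principal investigator's discretion (5.2.2).

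**Window without cyclosporine**
- End of window = 6 + 11/30.44 = 6.36 months after the test dose.
- Share of follow-up = 6.36/60 = 10.6%, or 6.36/72 = 8.8%.
- Time outside = 60 − 6.36 = 53.6 months, or 72 − 6.36 = 65.6 months.
- The 12-month visit may fall as early as month 10 (±2 months), so every visit from that one on lies outside the window.

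**Window with cyclosporine** (start and duration are assumptions)

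| Cyclosporine | Window ends (month) | Share of 60 | Share of 72 |
|---|---|---|---|
| from month 6, for 3 months | 6 + 3 + 6 = 15 | 25% | 21% |
| from month 12, for 12 months | 12 + 12 + 6 = 30 | 50% | 42% |

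**Illustration of missed events.** The documents give no late-event rate. Assume a constant annual rate r of a non-serious event and no attrition. Among subjects with at least one such event by month T, the share whose first event falls inside the window is

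(1 − exp(−r × 6.36/12)) / (1 − exp(−r × T/12)).

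For r = 0.05 and T = 60 this is 0.0262/0.2212 = 11.8%. For r from 0.01 to 0.10 it runs from 10.8% to 13.1% at T = 60, and from 9.1% to 11.4% at T = 72. These figures describe subjects not given cyclosporine who stay to the end.

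**What is captured after the window**

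| Late finding | Route in the plan |
|---|---|
| Serious adverse event, subject on study | Collected and reported (9.2.3) |
| Acute leukemia, progression, death | Endpoints (8.2.2, 8.2.4) |
| Annual thyroid, DAT, GPI-cell results | Measured (6.5); no analysis stated |
| Other non-serious adverse event | Medical record only (9.2.2) |
| Any event after leaving the study | Outside long-term collection; 8.6 provides for laboratory monitoring to 6 months off drug |

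**Who reaches late follow-up.** Section 8.3 plans 39 + 39 = 78 subjects. At its hypothesised 50% response, 78 × 0.5 = 39 would remain on study as responders, before any loss to death, withdrawal or cyclosporine failure.

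**The case against.** The strongest reply is that much of what matters is still caught. Serious events continue to be collected while a subject is on study, and the definition in 9.2.1 reaches beyond hospitalisation. Leukemia, progression and death are endpoints. The annual test results are study data, and nothing forbids summarising them. Adverse events are also summarised to the IRB at continuing review (9.2.4). All of this stands, and it confines the gap to non-serious events. It does not close it: the IRB summary is not an endpoint analysis, no section commits to analysing the annual tests, and a positive DAT or a thyroid abnormality managed without admission will often not be serious.

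A reader might go further and infer that the late-effects result will be almost empty, or that late effects as a whole will be understated. The documents do not support that, for the reasons just given. A reader might also conclude that 89% of safety follow-up is lost. That share fits only subjects not given cyclosporine who complete 60 months; it does not describe non-responders who leave early, and it measures calendar time rather than events.

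Nor do the documents show that most of the risk falls after the window. Section 2.7.1 places most infections in the first 8 weeks despite prolonged lymphopenia, and 2.6.3 does not expect GPI-deficient cells to be clinically significant. A 6-month cut-off for general adverse events is therefore a defensible choice.

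**Conclusion.** The point holds in limited form. The synopsis endpoint and the 9.2.2 cut-off do not fit together, and 8.2 supplies neither a definition nor an analysis to bridge them. The shortfall is non-serious late events in subjects still on study. For those never given cyclosporine who complete follow-up, about 6.4 of 60 months (10.6%) falls inside the window, or 8.8% if follow-up is 72 months. The share is larger for those given cyclosporine, by an amount that depends on when it starts and how long it lasts.

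The number of events missed cannot be derived from the documents; the 9–13% capture range rests on the assumed constant rates and no attrition. This is a modest weakness in a secondary endpoint. It does not touch the primary response analysis or the stopping rule.

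**What to change.** List late effects of treatment in 8.2, and say whether the endpoint covers all treated subjects, since the synopsis sentence can be read as limited to transfusion-dependent patients.

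In 9.2.2, keep the 6-month cut-off for general adverse events. Add that a short pre-listed set will be abstracted, from the medical record and the annual test results already obtained, to the end of each subject's follow-up:
- opportunistic infection;
- autoimmune cytopenia or new positive DAT;
- thyroid abnormality;
- expanded GPI-deficient population;
- lymphoproliferative disease or other malignancy.

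Report the set with person-time on study. State how many subjects left the study and when, and that those taken off study, chiefly non-responders, contribute little late follow-up, so the result applies mainly to responders. The change does not remove that selection; it makes it visible.

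**Cost.** Section 10.4 says that from January 27, 2017 the study is in data analysis only, so this is retrospective abstraction, with no new tests or visits. It takes some staff time, and records from home physicians may be incomplete, which should be stated with the result.
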